9.1. Sample Size Determination

The primary endpoint is the SADE incidence at 28 days of VIBLOK usage.

With a sample size of 36, an exact two-sided 95.0% confidence interval for a single proportion will show that the SADE incidence is below 10% at an expected incidence of 0.1%. Taking into account a drop-out rate of 15%, the estimated sample size needed is 42 study participants applying the VIBLOK cream.

The secondary endpoint is VIBLOK performance.

Statistical analysis will evaluate whether the disagreement rate in positivity between the pre- and post-treatment swabs is indicative of a decrease in detection frequency. For each person, the number of swabs on which shedding occurs only pre-intervention will be assessed, and then the number of swabs on which shedding occurs only post-intervention will be subtracted. If this number averages above zero, it indicates that the detection rate is decreased following intervention, and therefore a protective effect of the intervention with regard to shedding. Since this number is not distributed according to a known distribution, we will compare it to zero using a non-parametric test, the Wilcoxon signed-rank test. With an 8% anticipated asymptomatic shedding rate, 80% power and type I error of 5%, 40 participants taking samples for 28 days are needed to show a 50% reduction post-intervention, i.e. after applying VIBLOK.

Taking into account a drop-out rate of 15%, up to 46 adults applying VIBLOK cream are needed.

Total number of subjects to be enrolled.

Taking into account an overall screenfailure rate of 45% for absence of a confirmed HSV-2 infection, up to 84 subjects will be enrolled to get to the required minimum of 46 adults applying VIBLOK.

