After the examination, the participant will receive instructions by the site research staff as to how to take swabs and to apply VIBLOK, watch the instruction video, and subsequently takes the first swab, applies VIBLOK, and takes a second swab 5-60 minutes after applying VIBLOK while at the research site. These procedures will be monitored by one person from the site research staff to ascertain that the cream was applied correctly and that the swabs were obtained in the right way. Participants will also be instructed in how to label the swabs and vials. Once the swabbing procedures are correctly done, the participant will be provided the following:

- The study device along with instructions for use;
- The swabbing kits along with instructions for use;
- Diary.

Participants with a negative HSV-2 serology will be considered screen failures and exit the study.

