5.3.1. Missed Visits

Participants who miss a follow-up visit will not be considered to be withdrawn from the trial and contact with the participant should continue to be established for the follow-up examinations if applicable. Every participant that started applying VIBLOK, should be encouraged to remain in the study until they have completed the protocol-required follow-up period. If the participant discontinues prematurely from the study, the reason for discontinuation must be documented on the appropriate case report form (CRF). Possible reasons for premature discontinuation may include, but are not limited to the following:

- Withdrawal of consent: Participant decides to withdraw from the study. If a participant withdraws from the clinical investigation, the reason(s) should be recorded. If such withdrawal is due to problems related to the investigational device safety, the investigator shall ask for the participant's permission to follow his/her status/condition outside the investigation.
- Lost to follow-up – All participants should be encouraged to return to the clinic for evaluation during follow-up. If a participant is unable to return to the clinic, 3 separate telephone calls (or emails) should be made to attempt to bring the participant back into the clinic or obtain safety information. All attempts should be documented in the source documents. If the participant does not respond to the 3 telephone calls then the Investigator should send a certified letter to the participant. If applicable, a new round of attempts to contact the participant for return to the clinic for evaluation should be made when the subsequent visit is due.

Patients who discontinue prematurely will be included in the analysis of results, and will not be replaced.

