9.3. Analysis Sets

The *As Treated (AT) Population* will consist of all participants that were enrolled in the trial and that applied VIBLOK at least once.

The *Per Protocol (PP) Population* will consist of all participants who fulfil the protocol in the terms of the eligibility and that applied VIBLOK for at least 26 days.

The primary and secondary endpoints will be reported based on the AT population.

Descriptive and summary statistical analysis will also be performed on all primary and secondary endpoints on the PP population.

Prior to final statistical analysis, designated staff will develop a memo that describes the exclusions from analysis populations.

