#### Total number of participants to be enrolled

Taking into account an overall screening failure rate of 45% for absence of a confirmed HSV-2 infection, up to 84 participants will be enrolled to get to the required minimum of 46 adults applying VIBLOK.

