##### HSV-2 copy number on HSV DNA positive samples detected by quantitative real-time

The difference of the mean PCR HSV-2 copy number on days with asymptomatic shedding occurring only pre-intervention and occurring only post-intervention will be compared to zero using the non-parametric Wilcoxon signed-rank test.

Both analyses will be based on the As Treated Population and repeated for the Per Protocol Population.

Exploratory Poisson regression analyses may also be performed exploring the effect of other covariates like center, age and gender.

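### For the performance test, 46 treated participants cover a drop-out rate of 13.0%, not the stated 15%, on the 40 that the calculation requires

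*Protocol*

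**What the plan says.** For the performance endpoint, Protocol 9.1 gives the base number: "40 participants taking samples for 28 days are needed to show a 50% reduction post-intervention". This assumes 8% asymptomatic shedding, 80% power and a 5% type I error. The allowance for losses follows: "Taking into account a drop-out rate of 15%, up to 46 adults applying VIBLOK cream are needed". SAP 1.4 repeats both statements. The synopsis gives the same 40, 15% and 46 without the number of sampling days. No inflation formula is printed anywhere.

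The next step allows for 45% screen failure: "up to 84 subjects will be enrolled to get to the required minimum of 46 adults applying VIBLOK". The SAP has the same step: "up to 84 participants will be enrolled to get to the required minimum of 46 adults applying VIBLOK".

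Three other provisions determine how much this matters:
- Protocol 5.3.1: "Patients who discontinue prematurely will be included in the analysis of results, and will not be replaced".
- Protocol 9.3: "The primary and secondary endpoints will be reported based on the AT population". SAP 4.2.2 says of the two performance analyses: "Both analyses will be based on the As Treated Population and repeated for the Per Protocol Population".
- At Visit 1 (Protocol 5.2.3) the participant "takes the first swab, applies VIBLOK, and takes a second swab 5-60 minutes after applying VIBLOK while at the research site".

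**The concern.** An allowance for drop-out should leave the required number after the loss. The loss applies to those treated, so the required number is divided by the proportion retained. Here 46 matches the required number increased by 15%, which is a different operation and always gives too few. The same section handles the next loss, screen failure, by division, so two loss allowances a few lines apart follow different rules.

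What is at stake is whether the stated 46 supports its own sentence. The plan treats 46 as a required minimum, derives the enrolment figure of 84 from it, and does not replace participants who discontinue. Nothing later in the plan restores a shortfall.

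**Working it through.** **Inputs** (Protocol 9.1, repeated in SAP 1.4): required number 40, drop-out 15%, treated 46, screen failure 45%, enrolled 84. The 40 is taken as given. The documents state neither the between-person variation nor the pre/post correlation needed to rebuild the signed-rank power.

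**Reproducing the plan's figure**
- Required × (1 + drop-out) = 40 × 1.15 = 46.0, an exact match.
- Required / (1 − drop-out) = 40/0.85 = 47.06, which is not 46.

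**What 46 delivers**
- Expected to remain at 15%: 46 × 0.85 = 39.1, which is 0.9 below 40.
- Drop-out rate at which 40 remain: (46 − 40)/46 = 6/46 = 13.0%.
- Expected to remain of 46 at other assumed rates: 41.4 at 10%, 40.0 at 13%, 36.8 at 20%.

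**What 15% would need**
- 47 treated leave 47 × 0.85 = 39.95, which is 40 to the nearest person.
- 48 treated leave 48 × 0.85 = 40.8, the first whole number with an expectation of at least 40.
- These are averages. If participants drop out independently at 15%, the chance that 40 or more remain is 45% with 46 treated, 59% with 47 and 71% with 48.

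**The screen-failure step**
- Division: 46/0.55 = 83.6, rounded up to the stated 84.
- Multiplication would give 46 × 1.45 = 66.7. The plan therefore divides here.

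**The 42 for the primary endpoint**
- 36 × 1.15 = 41.4, rounded up to 42.
- 36/0.85 = 42.35, which is 42 to the nearest whole number.
- Either rule can give 42, so this figure does not show which was used.

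**The primary criterion** (SAP 5.2.1: exact two-sided 95% upper limit below 10%)
- With no SADE the limit is 1 − 0.025^(1/n): 7.71% at n = 46 and 9.03% at n = 39. Both pass.
- With one SADE the limit is 11.53% at n = 46 and 13.48% at n = 39. Both fail, and n would have to reach 54 to pass.
- Success therefore requires zero SADEs at 39, 46 or 48 alike.

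**The case against.** The strongest reply is that the number analysed does not fall to 39. The As Treated set holds everyone who applied the cream at least once, discontinuers are included, and the first swab pair is taken at the site. All 46 should therefore contribute a difference to the main performance test, and the disputed sentence never speaks of completers. This stands, and it keeps the point small. It does not make the allowance correct. The 40 is specified with 28 days of sampling, and someone who leaves early supplies less than that. Nor can days of swabs be pooled to replace a missing person, because the signed-rank test takes one difference per participant. The repeat in the Per Protocol set, which needs at least 26 days of application, also loses anyone who stops before then.

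A second reply is that multiplication is only inferred. That is right, because no formula is printed. The inference rests on the exact match and on the contrast with the screen-failure step, and the 42 adds nothing to it. The shortfall itself does not depend on the inference: 46 × 0.85 is 39.1 however 46 was reached.

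A third reply is that rounding matters, and with 47 counted as enough the plan is only one participant short. This is fair. The gap is one or two treated participants.

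**Conclusion.** The point holds as a minor arithmetic error. At the plan's own 15%, the 46 stated in the synopsis, Protocol 9.1 and SAP 1.4 leaves about 39 fully sampled participants where 40 are required. The 46 matches its sentence only up to a drop-out rate of 13.0%. This rests on the stated 40, 15% and 46, and on reading drop-out as a loss from those treated. The arithmetic is certain, while the cause (multiplication) is inferred.

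A reader might go further in three ways that the documents do not support.
- **The performance test is materially underpowered.** The shortfall is about one participant with full sampling, discontinuers stay in the main analysis, and the inputs needed to recompute the 80% are not given.
- **The safety conclusion is at risk.** The primary criterion passes with no SADE and fails with one, at 39 as at 46.
- **The primary endpoint's 42 repeats the error.** It fits either rule, and it does not set the sample size because 46 is larger.

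**What to change.** Keep 46 and 84. In the Protocol synopsis, Protocol 9.1 and SAP 1.4, replace the drop-out sentence for the performance endpoint with wording such as:

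> The trial will treat 46 participants. This retains 40 with full sampling at a drop-out rate of up to 13%; at 15%, about 39 are expected, one fewer than the 40 on which the 80% power is based. Participants who discontinue remain in the As Treated analysis.

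This still states where 46 stands relative to 40, so the screen-failure sentence that follows continues to make sense. The last sentence of the wording restates Protocol 5.3.1 and adds no new data rule; SAP 2.9 leaves the handling of drop-outs and incomplete data to a separate plan. Add no power figure unless the sponsor's statistician reruns the sponsor's own calculation at 39. Leave 42 as it is.

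The cost is a slightly less favourable stated figure and a text edit to both documents. A Protocol edit goes through the amendment procedure in Protocol 11.6, so it can wait for the next amendment. No analysis changes. Holding to 40 at 15% would instead take 47 treated and 86 enrolled (47/0.55 = 85.5), or 48 treated and 88 enrolled (48/0.55 = 87.3). Given the As Treated analysis, that is not asked for.

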Background	
Genital herpes has a high prevalence in industrialized as well as developing countries.
 
Genital herpes causes genital ulcers, increases risk for acquiring HIV infection, and may be transmitted mother to child during birth with possible serious consequences.
 
Medical treatments and condoms only partially reduce the risk for transmission from/ to sexual partners. Genital herpes transmission despite use of condoms is thought to be due to transfer via skin-to-skin contact in unprotected areas, and HSV-2 transmission may be enhanced by current shaving habits in the genital area leading to micro lesions (lacerations) of the skin.
 
VIBLOK™ is a cream designed to impede the passage of viruses, such as HSV-2, across the skin. Bench and animal experiments indicate that it can block virus transmission (HIV, HPV, HSV) up to 98%.
 
The objective of this clinical trial is to assess the safety and performance of VIBLOK in adults with HSV-2 infection by comparing virus detection in the extra-genital area before and after application of the barrier cream.

Primary objective	To assess safety of VIBLOK in HSV-2 infected adults.
Secondary objective	To evaluate the performance of VIBLOK as a barrier for virus transmission in men and women.
Study design	The VIBLOK SAfety and perFormancE Trial is a prospective, non-randomized, comparative multi-center safety and performance study. Up to 84 adults with a suspected HSV-2 infection are planned to be enrolled at up to 6 participating investigational centers in The Netherlands and Germany. Participants with a confirmed HSV-2 infection are planned to be followed for 26-31 days, using VIBLOK for minimally 26 days in a row. Safety will be assessed by collecting all adverse events, and HSV will be measured from daily self-collected external genital swabs before and after application of VIBLOK.
Study device	VIBLOK cream
Study scope	Minimally 1 and maximally 6 sites in The Netherlands and Germany are

	planned to participate in this study.
Study duration	The study is anticipated to last 12 months from first-subject-in to last-subject-out. Study participants are planned to be followed for 26 to 31 days.
Study Population	Adults with recurrent genital HSV-2 infections that meet all the inclusion and none of the exclusion criteria.
Number of subjects	Up to 84 men and women are to be enrolled, ensuring 46 participants with confirmed eligibility applying VIBLOK.

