Subject visits	
  
 Visit	Exams	Visit window	
   
 0	Screening	Subject information and consent	
 
 1	Day 1	<21 days after ICF sign off	
 
 N/A	Day 3	2-5 days following visit 1	
 
 2	Day 14	12-16 days following Visit 1	
 
 3	Day 28	26-31 days following Visit 1	
  
						Visit	Exams	Visit window	0	Screening	Subject information and consent	1	Day 1	<21 days after ICF sign off	N/A	Day 3	2-5 days following visit 1	2	Day 14	12-16 days following Visit 1	3	Day 28	26-31 days following Visit 1																																																																		
Visit	Exams	Visit window																																																																																								
0	Screening	Subject information and consent																																																																																								
1	Day 1	<21 days after ICF sign off																																																																																								
N/A	Day 3	2-5 days following visit 1																																																																																								
2	Day 14	12-16 days following Visit 1																																																																																								
3	Day 28	26-31 days following Visit 1																																																																																								

Statistical analyses	
With a sample size of 36, an exact two-sided 95.0% confidence interval for a single proportion will show that the SADE incidence is below 10% at an expected incidence of 0.1%. Taking into account a drop-out rate of 15%, the estimated sample size needed is 42 study participants applying the VIBLOK cream.
 
Comparing HSV-2 detection within participants before and after applying VIBLOK using Wilcoxon signed rank testing, with an 8% anticipated asymptomatic shedding rate, 80% power and type I error of 5%, 40 participants are needed to show a 50% reduction post-intervention (VIBLOK).
 
Taking into account a drop-out rate of 15%, up to 46 adults applying VIBLOK cream are needed.
 
Taking into account a screenfailure rate of 45% due to absence of an HSV-2 infection, up to 84 subjects will need to be enrolled.

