5.2.2. Participant Screening - Visit 0-1

The screening of potential participants will be conducted by one or more study team members. The site research team will be responsible for ensuring and reporting screening of men and women for study eligibility. Cumulative screening and enrollment logs will be maintained by research sites. Reasons for screen failures will be documented in study logs.

All anti-viral therapies shall be stopped minimally 7 days prior to Visit 1.

Women that are more than 1 year post-menopausal will be considered as having no child bearing potential, and the pregnancy test and use of contraceptives is not applicable for them.

Table 2 lists the schedule of events for participants from the initial screening and baseline measures through their bi-weekly follow-up visits. These measures are more fully described in the subsequent sections.

Table 2. Schedule of Events

Activity	Treatment Period				
	Screening	Visit 1	FUP call	Visit 2	Visit 3
Informed Consent	X				
Review Inclusion/Exclusion Criteria	X				
Medical History (including HSV history)	X				
Interim History (including HSV history)		X		X	X
Targeted Physical Exam (including external genital exam)	X	X*		X*	X*
HSV serology	X				
Urine pregnancy test	X				
Provide Study Device and/or training		X	X	X	
Review device use adherence				X	X
AE assessment				→	
User Questionnaire					X
Daily Swab Collection & Diary				→	

* for women possibly including internal genital exam if symptomatic

The following screening data will be collected for all study subjects prior to enrollment to assess possible eligibility:

- Medical history, standard of care physical examination, including external genital exam

A subject will be considered as "enrolled", once (s)he has signed the Informed Consent. Study

specific data will not be collected for subjects who fail any of the eligibility criteria and do not apply the study product; these subjects will be recorded on a Screening Log where the reason for screening failure will be documented.

5.2.3. Treatment start - Visit 1

Once participant's eligibility is confirmed, i.e. HSV-2 serology is positive, select assessments and laboratory tests will be done prior to document baseline status. These include:

- Physical examination, including a genital examination that for women may include an internal genital examination if symptomatic;
- (Interim) medical history;
- Urine pregnancy test;
- Adverse Events assessment

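### The limit of 84 consents yields 46 treated participants on average; at the plan's own 45% screen-failure rate it reaches 46 with 56% probability, so 46 is not an assured minimum

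*Protocol*

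**What the plan says.** Protocol section 9.1 derives the enrolment number from a screen-failure allowance, "Taking into account an overall screenfailure rate of 45% for absence of a confirmed HSV-2 infection", and concludes that "up to 84 subjects will be enrolled to get to the required minimum of 46 adults applying VIBLOK". The SAP, under its heading on the total number of participants to be enrolled, says the same: "up to 84 participants will be enrolled to get to the required minimum of 46 adults applying VIBLOK". The synopsis (Number of subjects) is firmer: "Up to 84 men and women are to be enrolled, ensuring 46 participants with confirmed eligibility applying VIBLOK".

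A person counts as enrolled "once (s)he has signed the Informed Consent" (Protocol 5.2.2). Seronegative subjects therefore use up places among the 84. Protocol 5.3.1 adds that participants who discontinue early are analysed and not replaced. Neither document says that consenting may continue past 84 if fewer than 46 have been treated.

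The 46 comes from the performance calculation in 9.1, where 40 participants are needed for 80% power: "Taking into account a drop-out rate of 15%, up to 46 adults applying VIBLOK cream are needed". The same sentence stands in the synopsis and in SAP 1.4. For the primary safety endpoint, 9.1 needs 36 participants and, after drop-out, "the estimated sample size needed is 42 study participants applying the VIBLOK cream".

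**The concern.** Dividing a target by the expected pass rate gives the number of consents at which the target is met on average. That is a reasonable planning figure. It becomes a problem when it is also written as an upper limit and the target is called a minimum, because the number who pass screening varies and there is almost no margin above 46.

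At stake is whether the ethics committee and the sponsor are told correctly what the design delivers. A shortfall would fall mainly on the performance comparison, which sets the larger sample size and is to support the CE-mark application. The text also describes 46 in two ways, as a number needed up to a limit and as a required minimum, so a reader cannot tell whether it is a target, a floor or a ceiling.

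**Working it through.** **Inputs**
- Target treated: 46 (Protocol 9.1; SAP 1.4).
- Screen-failure rate: 45%, so the chance that a consented subject goes on to apply the cream is 1 − 0.45 = 0.55 (Protocol 9.1).
- Limit on consents: 84, screen failures included (Protocol 9.1 and 5.2.2).
- Other reference numbers in 9.1: 36 and 42 (primary endpoint, before and after drop-out) and 40 (performance, before drop-out).

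**The plan's own figure**

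46/0.55 = 83.6, rounded up to 84. It reproduces.

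**What 84 consents deliver**

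Let X be the number treated, X ~ Binomial(84, 0.55).
- Mean: 84 × 0.55 = 46.2, which is 0.2 participants above the target.
- SD: √(84 × 0.55 × 0.45) = 4.6.
- 10th percentile: 40 treated.

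| Treated at least | What the number is | Exact probability |
|---|---|---|
| 46 | stated minimum | 0.562 |
| 42 | primary endpoint, after drop-out | 0.849 |
| 40 | performance, before drop-out | 0.929 |
| 36 | primary endpoint, before drop-out | 0.990 |

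The chance of missing 46 is 1 − 0.562 = 0.438.

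**Sensitivity to the screen-failure rate**

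The rates other than 45% are assumptions; the documents give no range.

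| Screen failure | P(X ≥ 46) with 84 consents |
|---|---|
| 40% (assumed) | 0.862 |
| 45% (plan) | 0.562 |
| 50% (assumed) | 0.223 |

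**Consents needed for a stated assurance of 46, at 45%**

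The smallest number giving P(X ≥ 46) of at least 0.80 is 90 (0.802), and of at least 0.90 is 94 (0.900).

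**The target itself**

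The 46 equals 40 × 1.15. Allowing for 15% drop-out among those who start means dividing by 0.85: 40/0.85 = 47.1, rounded up to 48. The matching expected number of consents is 48/0.55 = 87.3, rounded up to 88.

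**The case against.** The strongest reply is that there is no arithmetic error. Inflating by the expected pass rate is ordinary practice, and neither document claims a level of assurance. That stands: 84 is right as an expected-value figure. What remains is the wording built on it.

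A second reply is that 84 may not be a hard stop. Several passages call it planned enrolment, none says that recruitment closes at 84 with fewer than 46 treated, and Protocol 11.6 allows amendments. This stands in part. *Up to 84* reads naturally as a ceiling and nothing permits going past it, but the 56% depends on that reading.

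A third reply concerns impact, and most of it stands. Performance power rests on 40, not 46. The main analyses use everyone who applied the cream at least once (Protocol 9.3), so early leavers stay in, although they contribute fewer swab days. A reader might infer from the 56% that the trial is likely to be underpowered or that the primary endpoint is in danger. The documents do not support that: the chances of at least 40 and at least 36 treated are 93% and 99%.

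A reader might also infer that 56% is an upper bound, because the 45% is tied to absence of HSV-2 infection while subjects can fail on other criteria. The text does not settle this, since 9.1 also calls the rate overall. Finally, "up to 46 adults applying VIBLOK cream are needed" might be read as forbidding a 47th participant. It closes a calculation of need, and that reading is strained; the point is only that the descriptions of 46 differ.

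**Conclusion.** The concern holds as a mismatch between the wording and the plan's own inputs. With 84 as a ceiling on consents, exactly 45% screen failure and independent subjects, at least 46 are treated with probability 56%, and in about one case in ten 40 or fewer are treated. The synopsis cannot say that 84 ensures 46, and section 9.1 and the SAP cannot present 46 as a required minimum that 84 will meet.

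The consequence is moderate. It bears mainly on the margin for drop-out in the performance comparison, and hardly at all on the primary endpoint. The result is sensitive to the screen-failure rate: five percentage points either way move the chance of reaching 46 to 86% or 22%. No endpoint, analysis or success criterion is affected.

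**What to change.** 1. Settle the target first. Reconcile 46 with the stated 15% drop-out rate: 40/0.85 leads to 48, for which about 88 consents are expected.

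2. Preferably, define the end of recruitment by the number treated. Suggested wording: *consent continues until the target number of participants have applied VIBLOK; about 84 consents are expected for a target of 46*. If a limit on consents is still wanted, choose it for a stated assurance; for 46, 90 consents give 80% and 94 give 90%.

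3. Alternatively, keep the limit of 84. Replace *ensuring* in the synopsis, and *required minimum* in Protocol 9.1 and the SAP, with *expected to yield about 46*. State the 56% chance of 46 or more and the 10th percentile of 40.

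4. In either case, describe the treated number as a target, in the same words, in the synopsis, Protocol 9.1 and SAP 1.4.

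The cost is an edit to three places and, if recruitment ends on the treated count, possibly a few more consents and serology tests. With the target left at 46, no more participants are treated than planned; moving it to 48 would add two.
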